6.1.3 Study Drug End Days

For all subjects who receive at least one dose of study drug, study drug end days (days relative to the last dose of study drug) are calculated relative to the last dose of study drug. The last day of study drug is defined as Study Drug End Day 0. Days before it have negative study drug end days and days after it have positive study drug end days.

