6.2 Analysis Windows

For efficacy analyses of HCV RNA and resistance, the time windows specified in [Table 2](#) and [Table 3](#) describe how efficacy data are assigned to protocol-specified time points during the Treatment and PT Periods, respectively. All time points and corresponding time windows are defined based on the blood sample collection date.

For analyses of health-related quality of life (QoL) PROs collected throughout the study, the time windows specified in [Table 4](#) will be used.

For laboratory data and vital signs, the time windows specified in [Table 5](#) and [Table 6](#) describe how data are assigned to protocol specified time points during the Treatment and PT Periods, respectively.

If more than one assessment is included in a time window, the assessment closest to the nominal time will be used. If there are two observations equally distant to the nominal time, the latest one will be used in analyses. The only exception to this is for the SVR windows (e.g., SVR₄, SVR₁₂, and SVR₂₄); for these windows, the last value in the window will be used.

If multiple measurements are made on the same day for a safety laboratory parameter or a vital sign parameter, the average of the values will be used in analyses. For summaries of shifts from baseline and potentially significant values, multiple values on the same day will not be averaged; all values will be considered for these analyses.

Table 2. Analysis Time Windows for HCV RNA and Resistance Endpoints (Treatment Period)

Scheduled Visit	Nominal Day (Study Day)	Time Window (Study Day Range)
Day 1/Baseline ^a	1a	≤ 1 ^a
Week 2	14	2 to 21
Week 4	28	22 to 56
Week 12	84	57 to 126
Week 24 ^b	168	127 to 182
Final Treatment Visit ^c		2 to ≤ 2 days after last dose of study drug

a. Day of first dose of study drug.

b. Week 24 Visit is only applicable to subjects assigned to 24 weeks of treatment.

c. The last value within the window will be used to define the Final Treatment visit value.

Note: Data must also have Study Drug End Day ≤ 2 for all windows. The result closest to the scheduled time point will be used.

Table 3. Analysis Time Windows for HCV RNA and Resistance Endpoints (Post-Treatment Period)

Scheduled Visit^a	Nominal Day (Study Drug End Day)	Time Window (Study Drug End Day Range)
Post-Treatment Week 4	28	3 to 56
Post-Treatment Week 12	84	57 to 126
Post-Treatment Week 24	168	127 to 266
Post-Treatment Week 52	364	267 to 546
Post-Treatment Week 104	728	547 to 910

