6.3 Missing Data Imputation

No data will be imputed for any efficacy or safety analyses except for the PRO questionnaires, for analyses of the HCV RNA endpoints, and for analysis of the persistence of resistance. If a respondent answers at least 50% of the items in a multi-item scale of the SF-36v2, the missing items will be imputed with the average score of the answered items in the same scale. In cases where the respondent did not answer at least 50% of the items, the score for that domain will be considered missing. Similarly, the missing items of the FACIT-F questionnaire will be imputed with the average score of the answered items in the same scale as long as more than 50% (≥ 7 out of 13) of the items in the scale are answered. The SF-36v2 Mental and Physical Component Summary measures will not be computed if any domain is missing.

HCV RNA values will be selected for an SVR analysis based on visit windows as defined in Section 6.2. When there is no HCV RNA value in a visit window based on defined visit windows, the closest values before and after the window, regardless of the value chosen for the subsequent and preceding window, will be used for the flanking imputation described below.

If a subject has a missing HCV RNA value at a post-Day 1 visit but with undetectable or unquantifiable HCV RNA levels at both the preceding value and succeeding value, the HCV RNA level will be considered undetectable or unquantifiable, respectively, at this visit for this subject. In addition, if a subject has an unquantifiable HCV RNA level at the preceding value and an undetectable HCV RNA level at the succeeding value, or vice versa, the HCV RNA level will be imputed as unquantifiable at this visit for this subject. For SVR analyses, if there is no value in the appropriate window after flanking imputation but there is an HCV RNA value after the window, then it will be imputed into the SVR window. Subsequent to this flanking and backward imputation, if a subject is missing a value for the visit window associated with the analysis, the subject will be imputed as a visit failure (i.e., not undetectable or unquantifiable).

If a subject starts another treatment for HCV, then all HCV RNA and PRO assessment values for this subject measured on or after the start date of the new HCV treatment will be excluded from analyses. The subject will be considered a failure for summaries of viral response at all time points after the start of the new HCV treatment.

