Breakthrough = confirmed HCV RNA \geq LLOQ after HCV RNA < LLOQ during treatment, or confirmed increase from nadir in HCV RNA (two consecutive HCV RNA measurements > 1 log₁₀ IU/mL above nadir) at any time point during treatment. A single breakthrough value (\geq LLOQ or > 1 log₁₀ IU/mL above nadir) followed by lost to follow-up will be considered a breakthrough (i.e., will not require confirmation).

On-treatment virologic failure = breakthrough or failure to suppress during treatment (all on-treatment values of HCV RNA \geq LLOQ) with at least 6 weeks (defined as study drug duration \geq 36 days) of treatment.

RVR (rapid virologic response) = HCV RNA < LLOQ in the Week 4 window.

EOTR (end of treatment response) = HCV RNA < LLOQ in the Week 12 window for subjects receiving 12 weeks of treatment and in the Week 24 window for subjects receiving 24 weeks of treatment.

SVR₄ = HCV RNA < LLOQ in the SVR₄ window (4 weeks after the last actual dose of study drug) without any confirmed quantifiable (\geq LLOQ) post-treatment value during that SVR window.

SVR₁₂ = HCV RNA < LLOQ in the SVR₁₂ window (12 weeks after the last actual dose of study drug) without any confirmed quantifiable (\geq LLOQ) post-treatment value before or during that SVR window.

SVR₂₄ = HCV RNA < LLOQ in the SVR₂₄ window (24 weeks after the last actual dose of study drug) without any confirmed quantifiable (\geq LLOQ) post-treatment value before or during that SVR window.

Relapse₁₂ = confirmed HCV RNA \geq LLOQ between end of treatment and 12 weeks after last actual dose of active study drug (up to and including the SVR₁₂ assessment time point) for a subject with HCV RNA < LLOQ at Final Treatment Visit who completes treatment.

Relapse₂₄ = confirmed HCV RNA \geq LLOQ during SVR₂₄ window among subjects who achieved SVR₁₂ and have data available during the SVR₂₄ window.

Relapse_{late} = confirmed HCV RNA \geq LLOQ at any time after the SVR₂₄ assessment time point for a subject who achieved SVR₂₄ and has post-SVR₂₄ HCV RNA data available.

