10.8 Resistance Analyses

If possible, subjects treated with study drug who experience virologic failure will have resistance testing conducted if 1) they have on-treatment breakthrough; 2) if they have post-treatment relapse, with a study drug duration ≥ 77 days for subjects assigned to 12 weeks of treatment or with a study drug duration ≥ 154 days for subjects assigned to 24 weeks of treatment; or 3) if they have at least 6 weeks of treatment and fail to suppress by Week 6 (i.e., meet virologic stopping criteria). Subjects meeting one of these criteria will be referred to as subjects in the primary virologic failure (PVF) population, and a listing by subject that includes HCV subtype, IL28B genotype, reason for non-response, time point(s) sequenced as closest to time of VF, and HCV RNA value at the VF time point(s) will be produced for these subjects. In addition, all listings described below will display HCV subtype and reason for non-response in the subject identifier for each subject. A separate listing will delineate all subjects in the PVF population for whom no sequencing was performed (e.g., lost to follow-up while HCV RNA ≤ 1000 IU/mL).

Only samples with an HCV RNA level of ≥ 1000 IU/mL will undergo sequence analysis in order to allow accurate assessment of products of amplification. Therefore if the HCV RNA level at the time of virologic failure (VF) is < 1000 IU/mL, the sample closest in time after the failure with an HCV RNA level ≥ 1000 IU/mL will be used if available.

The regions of interest for next generation sequencing (NGS) from all evaluated time points in this study are those encoding full length NS3/4A, NS5A, and NS5B. The prototypic reference sequences used for analysis will be H77 for genotype 1a or Con1 for genotype 1b.

For each DAA target, resistance-associated amino acid variants will be identified by AbbVie Clinical Virology. Amino acid positions where resistance associated variants have been identified in vitro and/or in vivo are 1) for ABT-450: 36, 43, 55, 56, 80, 155,

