The number and percentage of subjects with post-baseline variants at signature amino acid positions or emerged variants at non-signature amino acid positions by, listed by amino acid position and variant within a DAA target at the time of VF compared to baseline will be summarized, along with the number of subjects within a DAA target and overall. The analyses will be grouped by HCV subtype (1a or 1b) and DAA target (NS3, NS5A, or NS5B) and will list the subject numbers of subjects with each variant. The number of subjects with resistance variants in 3 targets, 2 targets or 1 target will be provided.

Listings by subject and time point of all post-baseline variants relative to the baseline amino acid sequence will be provided for each DAA target (NS3, NS5A, and NS5B). In addition, a listing by subject and time point of all post-baseline variants at signature resistance-associated amino acid positions relative to the appropriate prototypic reference amino acid sequences will be provided.

For all subjects who experience VF, the persistence of resistance-associated variants for each target (NS3, NS5A, and NS5B) will be assessed by NGS at Post-Treatment Weeks 24 and 52 and at time points up to Post-Treatment Week 260 (5 years). The number and percentage of subjects with post-baseline variants at signature amino acid positions, listed by amino acid position and variant within a DAA target at each Post-Treatment time point compared to baseline will be summarized, along with the number of subjects within a DAA target and overall. Additionally, the number and percentage of subjects in whom a signature variant persisted at Post-Treatment Week 24 and 52 and time points up to Post-Treatment Week 260 (5 years) out of the total number of subjects with that emerged variant at the VF time point and at that time point will be summarized by DAA target, and variant. The number and percentage of subjects who still have a variant at a given Post-Treatment time point will be calculated out of all subjects with that variant at VF who have sequencing at that time point. The imputation described below will be used for PT Week 52 or time points up to Post-Treatment Week 260 (5 years). If a

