signature variant is not detectable at Post-Treatment Week 24, the variant is imputed as not detectable at the Post-Treatment Week 52 and time points thereafter even if a sample from Post-Treatment Week 52 or later is not sequenced. If a signature variant is detectable at Post-Treatment Week 52 or later, then the variant is imputed as being detectable at earlier time points even if the sample at the earlier time point is not sequenced.

If resistance-associated variants are not detected by NGS in a given target for a subject either at the time of failure or in a post treatment sample, then that target will not be sequenced in subsequent samples from that subject.

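### The resistance-persistence rules can count a late relapser's failure sample as persistence and impute the variant at visits before that subject had quantifiable virus

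*SAP*

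**What the plan says.** **Who is included.** SAP 10.8 states: "For all subjects who experience VF, the persistence of resistance-associated variants for each target (NS3, NS5A, and NS5B) will be assessed by NGS", at Post-Treatment (PT) Weeks 24 and 52 and on to Week 260. The relapse route into resistance testing reads "if they have post-treatment relapse, with a study drug duration" and goes on to set only a minimum treatment duration. It gives no latest date for the relapse. SAP 10.1 recognises relapse in the SVR24 window and also late relapse, "at any time after the SVR₂₄ assessment time point for a subject who achieved SVR₂₄". Protocol 8.1.3 likewise covers subjects who reach SVR12 and then lose it.

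**The clock.** SAP 6.1.3 sets time zero at the last dose: "The last day of study drug is defined as Study Drug End Day 0". SAP 6.2, Table 3 builds the post-treatment resistance windows on that scale: PT Week 24 is days 127 to 266, PT Week 52 is days 267 to 546, PT Week 104 is days 547 to 910, and so on.

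**What is sequenced.** SAP 10.8 sequences only samples with at least 1000 IU/mL. If HCV RNA at failure is lower, the nearest later sample that reaches the threshold serves as the VF sample.

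**Imputation.** SAP 10.8 says: "If a signature variant is detectable at Post-Treatment Week 52 or later, then the variant is imputed as being detectable at earlier time points", even where the earlier sample was not sequenced. SAP 6.3 carries the same rule. Neither section refers to the VF date or to HCV RNA at the earlier visit.

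**Denominator.** SAP 10.8 takes the percentage among subjects who had the variant at VF and were sequenced at the visit. Its next sentence applies the imputation to PT Week 52 through Week 260.

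**Retreatment.** Under SAP 6.3, once a new HCV treatment starts, "all HCV RNA and PRO assessment values for this subject measured on or after the start date of the new HCV treatment will be excluded". Sequences are not named.

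**The concern.** Persistence should mean that a variant seen at failure is still there some time later. That needs a second look after the failure sample. The rules as written do not require one, and for a late relapser they fill in visits that came before failure.

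Both effects can only raise the reported percentage, and they raise it most for variants that disappear quickly. The contrast between targets where variants fade and targets where they last would be blurred. The protocol (synopsis and 8.1.3) promises an evaluation of persistence over five years, and these percentages are its main summary.

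**Working it through.** The documents give no persistence rate and no count of late relapsers, so there is no stated figure to reproduce. The check is to apply the rules to example subjects and then show the arithmetic under stated assumptions.

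**Step 1: the failure sample as its own persistence.** Take a relapser whose VF sample is also the sample selected for the PT Week 24 or PT Week 52 window. The variant is present at VF and at the visit, from a single sample. The subject enters both numerator and denominator at zero weeks after failure. No imputation is involved, so the denominator conflict does not affect this. The SVR24 window (days 127 to 210) lies inside the PT Week 24 window (days 127 to 266), so a relapse in the SVR24 window can do this. So can a PT Week 12 relapse with HCV RNA below 1000 IU/mL, if its first sequenceable sample is at PT Week 24.

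**Step 2: back-fill before failure.** Each subject below has one sequenced sample, the failure sample, which carries the variant.

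| First viraemic | Sequenced | Imputed detectable (clear) | Imputed detectable (unclear) |
|---|---|---|---|
| PT Week 52 | Week 52 | none | Week 24 |
| PT Week 104 | Week 104 | Week 52 | Week 24 |
| PT Week 208 | Week 208 | Weeks 52, 104, 156 | Week 24 |

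The imputed visits were unsequenced because HCV RNA was below LLOQ. Week 24 is unclear because the rule speaks of earlier time points, while SAP 10.8 confines the imputation to PT Week 52 onward.

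**Step 3: the denominator.** Let E be early failures with the variant at VF, all sequenced at the visit. Let p be their true persistence, and k the further subjects whose VF sample is at or after the visit.

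- If only sequenced subjects count, those whose VF sample is after the visit drop out. Those whose VF sample is at the visit remain. The imputation then does nothing for this percentage.
- If imputed subjects count in both places, the reported value is (E·p + k)/(E + k).
- If imputed subjects count only in the numerator, the result can pass 100%. With E = 20, p = 0.8 and 5 back-filled subjects, (16 + 5)/20 = 105%.

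**Step 4: illustration.** Assume E = 30. A virologic failure rate of about 2%, itself an assumption, would give 0.02 × 1650 = 33 failures. Reported persistence is then (30p + k)/(30 + k):

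| True p | k = 1 | k = 3 | k = 6 |
|---|---|---|---|
| 10% | 12.9% | 18.2% | 25.0% |
| 50% | 51.6% | 54.5% | 58.3% |
| 90% | 90.3% | 90.9% | 91.7% |

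For example, p = 10% and k = 3 gives (3 + 3)/33 = 18.2%. SAP 10.8 reports by target and variant, so real denominators may be well below 30. With E = 10 and p = 10%, one such subject gives 2/11 = 18.2%. If visits at or before the VF sample are not counted, the k subjects drop out and the figure returns to p.

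**The case against.** The strongest reply is that the denominator sentence already protects the percentage: a late relapser not sequenced at an earlier visit is outside it. That would be enough if the next sentence did not apply the imputation. The two cannot both govern the same percentage, and the reply leaves Step 1 untouched.

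A second reply is that the SAP's language of variants persisting, and its separate mention of the VF time point and the visit, imply a later sample. That is a fair reading of the intent, but no rule enforces it.

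Several stronger readings are tempting, and the documents do not support them:

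- **Back-fill to every earlier visit.** Week 24 is doubtful for the reason given under Step 2. The clear case needs first viraemia at PT Week 104 or later.
- **Variants selected by a later HCV regimen counted as persistence.** The persisted percentage requires the variant at VF, so a newly selected variant cannot enter it; only re-selection of one already present could. The gap in the retreatment cut-off matters mainly for the by-visit table of post-baseline variants, which has no such condition.
- **No other record of persistence.** SAP 10.8 also provides listings by subject and time point, in which a late relapser would be visible.
- **Timing from last dose as an error in itself.** It follows the visit schedule, and timing everything from VF fits poorly with annual visits after PT Week 52.

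It is also true that back-fill is reasonable at visits after the VF sample, and that SAP 10.1 removes documented re-infections from the relapse analyses, which would lower k.

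**Conclusion.** The point holds as a minor one. For late relapsers the rules as written give a wrong value: persistence at zero weeks when the failure sample falls in a PT Week 24, 52 or later window, and an imputed variant while HCV RNA was below LLOQ when first viraemia is at PT Week 104 or later. The denominator wording in SAP 10.8 also contradicts the imputation that follows it.

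The bias is upward. Its size cannot be established, because the documents do not give the number or timing of late relapses. The move from 10% to 18.2% rests on assumed values of 30 early failures and three late ones. Of those three, any whose VF sample comes after the visit count only if imputed subjects enter the percentage. Where true persistence is 90%, the change is under 2 points even with six.

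The analysis is descriptive, is not a primary or secondary objective, and does not touch the primary endpoint.

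**What to change.** In SAP 10.8, with matching text in 6.3:

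- Keep the fixed post-treatment visits, but count a subject at a visit only if that visit is after the VF sample.
- Allow backward imputation only to unsequenced visits after the VF sample, never to a visit before VF or with HCV RNA below LLOQ. State whether PT Week 24 is in scope.
- State one population for both numerator and denominator: subjects with the variant at VF who are sequenced, or validly imputed, at a visit after the VF sample.
- Extend the SAP 6.3 retreatment cut-off to sequence data.
- Optionally, add a supplementary summary timed from the VF sample.

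The cost is SAP wording and programming. VF dates, HCV RNA and post-treatment HCV medications are already collected. The drawback is slightly smaller denominators at some visits.

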10.9 Patient Reported Outcomes

The following instruments will be used to collect patient reported outcomes (PROs): SF-36 version 2 (SF-36v2) and FACIT-F. Missing data for each measurement will be handled as described in Section 6.3.

The following exploratory analyses of PROs will be performed by baseline fibrosis stage:

- mean change from baseline to each applicable post-baseline time point in the SF-36v2 Mental Component Summary (MCS), Physical Component Summary (PCS) and eight individual domain measures;
- mean change from baseline to each applicable time point in the FACIT-F total score;
- percentage of subjects without a decrease from Baseline to Final Treatment Visit in the SF-36v2 PCS and MCS that is greater than or equal to the minimally important difference (MID) of five points.

The SF-36v2 measures dimensions of a patient's functional health and well-being in 8 domains and also provides 2 summary scores that characterize a patient's mental (MCS) and physical (PCS) health status. The score for each of the 8 domains ranges from 0 to 100 and will be normalized according to the user manual. The standardization of the normalized scores will provide the norm-based scores with a mean of 50 and a SD of 10.

The two summary scores are based on the norm-based scores. Per the SF-36v2 instrument manual, score for any item with multiple responses will be set to "missing." Subject's responses to the SF-36v2 will be summarized for the PCS and MCS measures.

The FACIT-F is a symptom specific instrument with a focus on measuring fatigue in a variety of chronic diseases or health conditions. Its 13-item-version assesses peripheral, central, or mixed fatigue and yields a summed total score ranging between 0 and 52. Higher FACIT-F scores indicate a lesser degree of fatigue. Notice that item 7 (I have energy) and item 8 (I am able to do my usual activities) are reverse scored.

Summary statistics (n, mean, SD, median, minimum and maximum) for the mean change from baseline to each applicable visit will be provided for the FACIT-F score and the SF-36v2 PCS and MCS scores.

In particular, an analysis of the mean change from baseline to Post-Treatment Week 12 and to Post Treatment Week 24 in the SF-36 V2 Vitality scale, Mental Component Summary score, Physical Component Summary score and FACIT-F score, will be performed using ANCOVA analyses with appropriate baseline fibrosis stage, SVR₁₂ status, and their interaction as factors, and baseline PRO score as covariate. A summary of the analysis results comparing subjects who have achieved SVR₁₂ and subjects who have not will be provided. A similar summary of analysis results comparing subjects with different fibrosis stage will be provided also. Additional analysis on the PRO data will be performed as useful and appropriate.

An MID of -5 will be used for the change from Baseline to Final Treatment Visit in the SF-36v2 PCS and MCS. The percentage of subjects with a change from Baseline to Final Treatment Visit > -5 will be presented along with 95% confidence intervals.

